#### **14.5 Notification of Serious Breaches to GCP and/or the protocol**

It is understood that “a serious violation” is likely to affect to a significant degree:

- the safety or physical or mental integrity of the Trial participants; or
- the scientific validity of the Trial

In that case, the Sponsor should be notified immediately upon becoming aware of a serious breach during the study conduct phase. The sponsor of a clinical will notify the licensing authority in writing of any serious breach of the conditions and principles of GCP in connection with that trial, or the protocol relating to that trial, as amended from time to time, within 7 days of becoming aware of that breach.

#### **14.6 Data protection and patient confidentiality**

All investigators and trial site staff must comply with the requirements of the Belgian and European Privacy legislation (<http://www.dataprotectionauthority.be/legislation-and-standards>) on the protection of privacy in relation to the processing of personal data, with regards to the collection, storage, processing and disclosure of personal information.

The investigator/delegate must ensure that data/patient confidentiality is maintained. On eCRFs or other documents (e.g., documents submitted to the EC or those attached to SAE forms) submitted to the sponsor, subjects must be identified only by number and never by their name or initials, date of birth, hospital numbers, or any other personal identifier. The investigator/delegate must keep a subject identification code list at the site, showing the subject number, the subject's name, date of birth, and address or any other locally accepted identifiers. Documents identifying the subjects (e.g., signed ICFs) must not be sent to the sponsor, and must be kept in strict confidence by the investigator/delegate.

#### **14.7 Financial and other competing interests for the chief investigator, PIs at each site and committee members for the overall trial management**

The Chief Investigator and PIs at each site and committee members of the overall trial management have no competing interest.

#### **14.8 Indemnity**

The Participating Site, the Investigator and Sponsor shall have and maintain in full force and effect during the term of this Trial, and for a reasonable period following termination of the Trial, adequate insurance coverage for: (i) medical professional and/or medical malpractice liability, and (ii) general liability.

##### ***For Belgian Participating Sites***

Art 29 of the Belgian Law relating to experiments on human persons dated May 7th, 2004 applies.

Prior to the start of the Trial, the Sponsor shall enter into an insurance contract in order to adequately cover Trial participants from Belgian sites in accordance with art. 29 of the said law.

### **For non-Belgian Participating Sites**

The Participating Site shall have and maintain in full force and effect during the term of this Trial (and for a reasonable period following termination of the Trial, adequate insurance coverage for other possible damages resulting from the Trial at the Participating Site, as required by local law. Each such insurance coverage shall be in amounts appropriate to the conduct of the services of the Participating Site under this Trial. The Participating Site and Sponsor shall be solely responsible for any deductible or self-insured retention under any such policies.

### **14.9 Access to the Study Data by KCE and similar institutes in the EU**

This section should be read in conjunction with the research agreement, which supersedes the protocol in case of contradictory statements.

A distinction is to be made by access by KCE (and similar institutes in Europe) and access by other parties.

**Access to Study Data by KCE** is fully defined in the contract between KCE and the Sponsor and the research agreement template is publicly available on the KCE website. Link: <https://kce.fgov.be/en/resources-for-investigators>

After the completion of the study the Sponsor will transfer the pseudonymised study data set to KCE. KCE will request approval from the competent chamber of the Information Security Committee (ISC) to have the relevant study data linked with e.g. IMA data by a trusted third party (TTP, eHealth platform) using the patient national number.

The patient information and consent includes wording that the national number will be recorded on site by the investigator for later data linkage, but will not be included in trial database available to the sponsor or any other third party. The patient information and consent will also include that in case the patient is randomized, it is planned that a trusted third party (TTP, eHealth platform) will receive and use the national number to link with IMA administrative data. To this end, KCE will receive the link between the study number and the national number under pseudonymised form. KCE will never be able to use the link without authorisation of the ISC and the intervention of the TTP. This data linkage is planned to obtain a more complete data set containing costs related to health care paid by the compulsory health insurance and the patient that will be used for the analysis of effectiveness and cost-effectiveness of the intervention by KCE. The processing of personal data for this analysis is necessary for the performance of a task carried out in the public interest, as specified in the law defining KCE's missions and tasks. To the extent the personal data is related to health, the processing is necessary for scientific or statistic purposes, as specified in the law defining KCE's missions and tasks. For all processing related to the analysis of effectiveness and cost-effectiveness of the intervention, KCE is the controller.

KCE and Sponsor have entered into a research agreement detailing the roles and responsibilities of each party, as well as other legal aspects of this collaboration, including the right to use and access of KCE to the Study Data.

“Background” means any intellectual property (IP), data, materials, information owned or controlled by the Sponsor or a Site, and required to run this Study. Sponsor will identify such Background including the legal restrictions of which Sponsor or Sites are aware that may affect the use of the Background for the purpose of the Study or the rights granted to KCE under this Agreement.

The Study Data consist of this protocol, including amendments, the electronic forms for data capture, including the annotations and guidance for use, the electronic database of the pseudonymized clinical and non-clinical data collected using data capture, including the log of changes from data entry to database

lock, study reports based on these pseudonymized data, and any data or reports generated at a later stage, e.g. based on exploratory analyses or stored samples.

“Foreground” means any Study Data, and any tangible biological, chemical and physical material and inventions, that are generated, acquired, discovered, conceived, developed, created, exemplified or derived as a result of carrying out the Clinical Study, whatever its form or nature, whether it can be protected or not, as well as any Foreground IP. Sponsor acknowledges that the main purpose of the research performed under this Agreement is to generate results that will serve the general public interests, and specifically the interests of the patients and public healthcare decision making bodies, and, therefore, undertakes not to exploit the Foreground in any way that is or could be detrimental to such interests.

The Sponsor owns the Study Data, but provides KCE with a copy of the pseudonymized database after database lock as well as a royalty-free unrestricted license to use the Study Data for non-commercial public health related purposes as detailed in the Agreement between KCE and <<Institution>> (details will be documented in the appropriate juridical documents). If judged appropriate, KCE will introduce the request to the competent chamber of the Information Security Committee and arrange for the data linkage. For the sake of clarity, the linked data are not part of the Study Data. However, KCE will discuss with the Sponsor the results of the analyses and the reporting of the linked data.

#### **14.10 Access to the final trial dataset by other parties**

The study results will be owned by the party who generates them. The Sponsor will have access to the study data. At the end of the study, KCE will receive from Sponsor specific study data. This will only be anonymous study data or, where requested by KCE, coded personal data are made available to KCE.

The study data shall not be provided to a third party without the prior written approval of KCE, which approval KCE shall not unreasonably withhold or delay and which KCE may subject to specific conditions in order to ensure that the provision of said study data does not have a negative impact on the further performance of the study, the rights granted to KCE under the research agreement and/or the benefit of the Study for the patients and/or the public payers.

### **15 DISSEMINATION POLICY**

#### **15.1 Dissemination policy**

This section should be read in conjunction with the research agreement, which supersedes the protocol in case of contradictory statements.

The Declaration of Helsinki (latest version) and European and Belgian regulations require that every research Trial involving human participants be registered in a publicly accessible database before recruitment of the first participant. The CI is responsible for registering the Trial.

In addition, the CI will fulfil their ethical obligation to disseminate and make the research results publicly available. As such the CI is accountable for the timeliness, completeness and accuracy of the reports. Researchers, authors, Sponsors, editors and publishers must adhere to accepted guidelines for ethical reporting. Negative and inconclusive, as well as positive results must be published or otherwise made publicly available. Sources of funding, institutional affiliations and conflicts of interest must be declared in publication.

#### **15.2 Authorship eligibility guidelines and any intended use of professional writers**

Publications will be coordinated by the CI. Authorship to publications will be determined in accordance with the requirements published by the International Committee of Medical Journal Editors and in accordance with the requirements of the respective medical journal.

For multicentre Trials, it is anticipated that the primary results of the overall Trial shall be published in a multicentre publication.

Participating Sites are not allowed to publish any subset data or results from the Trial prior to such multicentre publication.

Any publication by a Participating Site must be submitted to the Sponsor for review at least thirty (30) calendar days prior to submission or disclosure. Sponsor shall have the right to delay the projected publication for a period of up to three (3) months from the date of first submission to the Sponsor in order to enable the Sponsor to take steps to protect its intellectual property rights and know-how.

### 15.3 Communication plan

There is a consensus among experts that the results of clinical trials should be made available to participants and suggested that providing participants with results, both positive and negative, should be considered the “ethical norm”(119). This practice is being encouraged because it is a way of showing respect for research participants and to acknowledge the central role of participants in the completion of research studies. Communicating results avoids treating the participants as a means to an end (120). Although there are no strict guidelines formulated to share the results of trials with patients (121), the development of a communication plan is important. Therefore, a plan to communicate the results of the foot drop trial with all participants will be developed. Several barriers are taken into account:

1. Some patients might not want to know the results. Reactions to results may be influenced by an individual's coping style, how well he or she dealt with the foot drop. The response of the participant can also be affected by how the patient fared with the treatment. Patients may not want to know that they were allocated to the inferior arm of the trial. To address this concern, patients will be asked at the time of study enrollment if they wish to be offered trial results in the future. The informed consent form should both discuss potential benefits and risks of receiving results of the trial (122).
2. If the study participant has died or is not capable anymore of receiving the results himself or herself, psychosocial repercussions have to be anticipated when the family of the participant is contacted to discuss the results of the trial. Death or mental deterioration due to peroneal entrapment is not anticipated and highly unlikely.
3. The primary goal of clinical research is to seek generalizable knowledge. Physicians need to be aware that the results of the trial could not be beneficial for his/her own individual patient with whom he has a therapeutic relationship.
4. A fourth barrier is the absence of patient's groups. Therefore it is not possible to distribute trial specific information through patient group websites or patient communities, something that has been done in other trials (123).

Following guidelines to determine the appropriate time at which results would be offered to participants and to disseminate the plans are proposed. The proposed guidelines are partially based on the guidelines formulated by Fernandez et al. (124).

#### *Willingness to receive trial related information.*

Patients will be asked at the time of study enrollment if they wish to be offered trial results in the future. This will be included in the informed consent form. Both potential benefits and risks of receiving results of the trial will be discussed. If a patient chooses to not receive the trial results, this will be documented in the electronic case report form (eCRF). If a patient wants to receive the trial results, the patient can choose if he wants to be informed through e-mail or through a postal letter. If patients change their mind during the trial and choose to not receive the trial results, the study team can be addressed and the changes can be documented in the eCRF.

#### *Trial results of full-scale trial*

The results of the research will be communicated with the participants after all participants have reached the primary endpoint. This data will not be shared with participants until the data interpretation has undergone peer review. Research results should be offered in a timely manner and will therefore be

communicated within 1 month after the data are peer reviewed. Participants will receive an e-mail or postal letter that will address the following bullet points:

- The context and goals of the study will be documented, without the use of medical jargon.
- Major findings of the trial. The analyzed endpoints will be discussed.
- Limitations of the study.
- Any anticipated long-term effects
- Contact information of the site-specific clinical trial assistant will be provided to give participants the opportunity to ask for more / individualized information. This will also allow participants to receive additional information provided by the treating physician. This will allow to address medical or psychological needs of the research participants.
- The opportunity for patients will be provided to enlist to receive information on the extended follow-up period of 18 months. Only participants that want to receive additional information will receive this information. Results of the extended follow-up visit of 18 months will be communicated after the end of the trial, when all data have been analyzed and peer reviewed. These results will be made available within 3 months after this process.
- Gratitude towards the participants will be stressed in the communication.

Communication of results of the trial towards patients can be time consuming. Since the anticipated number of inclusions in the most centers is rather small, this should be feasible. The PI will be responsible for patient communication but can involve other staff or employees in a site-specific manner. In exceptional and unforeseen circumstances, bad information should always be discussed with the patient by the treating physician or PI.

## ■ APPENDICES

### APPENDIX 1. RISK ASSESSMENT OF THE TRIAL INTERVENTION(S)

Risks associated with trial interventions

- A ≡ Comparable to the risk of standard medical care**
- B ≡ Somewhat higher than the risk of standard medical care
- C ≡ Markedly higher than the risk of standard medical care

Justification: Briefly justify the risk category selected and your conclusions below (where the table is completed in detail the detail need not be repeated, however a summary should be given):

Both treatment arms are currently applied in daily clinical practice and application in this trial do not pose more than minimal additional risk or burden to the safety of the subjects compared to normal clinical practice.

## APPENDIX 2. AUTHORISATION OF PARTICIPATING SITES

### Appendix 2.1. Required documentation

- CV of the research team
- Certificate of good clinical practice (physicians)
- Confirmation of training of blinded researchers
- Confirmation of successful in training in REDCap data management

### Appendix 2.2. Procedure for initiating/opening a new site

If the go criterion is met during the feasibility pilot study, the foot drop trial will be extended to a full-scale study. More than 20 centers in Belgium and several centers in the Netherlands will be included.

### Appendix 2.3. Principal Investigator responsibilities

The PI's legal responsibilities will be listed in the clinical study agreement.

A PI is expected to:

- Attend the initiation meeting/teleconference
- Supervise the training of the team members / blinded outcome assessors
- Ensure that the ISF is accurately maintained
- Report safety within the timelines
- Disseminate important safety or trial related information to all stakeholders within their sites

## APPENDIX 3. AMENDMENT HISTORY

Amendment No.	Protocol version no.	Date issued	Author(s) of changes	Details of changes made
1	V.2.0	###	[name]	
Adaptation of protocol based on pilot study results. This amendment concerns minor protocol adaptations:
 

- Deletion of SF-36 as QOL questionnaire

- Deletion of ankle dorsiflexion range of motion as study assessment

 
The new recruitment strategy is included as well.

## APPENDIX 4. LIST OF STANDARD ASSESSMENTS

### MOTOR ASSESSMENT: MRC score for ankle dorsiflexion, ankle eversion and hallux-extension

Please use a score from 0 to 5 to grade the power of the muscle group in relation to the maximum expected for that muscle (compare to the contralateral healthy side).

Muscle group	MRC score (/5)
Ankle dorsiflexion	....
Ankle eversion	....
Hallux extension	....

### SENSORY FUNCTION

Symptoms qualified as sensory included the presence of hypoesthesia and/or paresthesia. Please use following system to assess sensory symptoms (compare to the contralateral healthy side):

- Complete recovery: the absence of any sensory symptoms
- Partial recovery: patients with a minimum of sensory symptoms
- No recovery: patients with no improvement

.....	.....	recovery
-------	-------	----------

### Ability to WALK BAREFOOT?

YES  NO

### Need for FOOT-ANKLE ORTHOSIS?

YES  NO

## TREATMENT RECORD

Physiotherapy: frequency	..... / week
Physiotherapy: duration per session	..... minutes
Additional Home exercises	Yes / No ..... / week (frequency)
Use of electrostimulation	Yes / No ..... / week (frequency)
Total number of physiotherapy sessions	..... sessions
Other therapies (e.g. vitamin substitution, acupuncture, ...)	.....

## APPENDIX 5. REFERENCE VALUES FOR 6-MINUTE WALK DISTANCE (6MWD) IN A NORMAL HEALTHY POPULATION

### Appendix 5.1. Reference values for 6MWD in a healthy population aged 20 to 80 years

	Subject Age		
	20–40 years	41–60 years	61–80 years
Men			
N	19	12	10
Best 6MWD	800 ± 83 m	*671 ± 56 m	*687 ± 89 m
Women			
N	15	13	10
Best 6MWD	†699 ± 37 m	†670 ± 85 m	583 ± 53 m

SD: standard deviation; WD: walking distance.  
 Group means ± SD. Single factor ANOVA found a significant difference in best 6MWD across age groups in men ( $F = 12.69, P < 0.0001$ ) and in women ( $F = 11.2, P < 0.0002$ ). Post-hoc comparisons using Tukey's test revealed that best 6MWD was significantly greater in younger men than in middle-aged and older men. Post-hoc comparisons using Tukey's test revealed that best 6MWD was significantly lower in older women than in middle-aged and younger women.

\* Significantly different from men aged 20 to 40 years.  
 † Significantly different from women aged 61 to 80 years.

Variable	Coefficient	Cumulative $r^2$	Individual P value
Age (years)	2.99	0.25	<0.0001
Gender	74.7	0.41	<0.0001

WD: walking distance.

The model predicts best 6MWD as:  $868.8 - (2.99 \times \text{Age}) - (74.7 \times \text{gender})$  where men = 0 and women = 1. Although height was significantly related to best 6MWD in univariate regression analysis, it did not improve cumulative  $r^2$  (individual  $P$  value  $< 0.97$ ) when included in the model.

Table 3 \* MULTIPLE LINEAR REGRESSION ANALYSIS OF BEST 6MWD

Reference values for the 6MWD per age-category as published by Gibbons et al. (60).

## APPENDIX 6. AGE AND SEX-BASED REFERENCE VALUES FOR GAIT SPEED

Table 2 - *Mean and standard error of estimate (SE) of walking speed (m·s) presented by gender and decade of age.*

Decade of age Years	Women		Men	
	Speed	SE	Speed	SE
20	1.50	0.106	1.56	0.147
30	1.49	0.093	1.55	0.136
40	1.47	0.136	1.48	0.125
50	1.43	0.192	1.46	0.147
60	1.42	0.105	1.46	0.187
70	1.30	0.174	1.36	0.184
80	1.18	0.136	1.25	0.185

Mean estimate of walking speed (m/s) presented by gender and decade of age (101).

## APPENDIX 7. WORK PRODUCTIVITY AND ACTIVITY IMPAIRMENT QUESTIONNAIRE: GENERAL HEALTH

### Work Productivity and Activity Impairment Questionnaire: General Health V2.0 (WPAI:GH)

The following questions ask about the effect of your health problems on your ability to work and perform regular activities. By health problems we mean any physical or emotional problem or symptom. *Please fill in the blanks or circle a number, as indicated.*

1. Are you currently employed (working for pay)?  NO  YES  
*If NO, check "NO" and skip to question 6.*

The next questions are about the **past seven days**, not including today.

2. During the past seven days, how many hours did you miss from work because of your health problems? *Include hours you missed on sick days, times you went in late, left early, etc., because of your health problems. Do not include time you missed to participate in this study.*

HOURS

3. During the past seven days, how many hours did you miss from work because of any other reason, such as vacation, holidays, time off to participate in this study?

HOURS

[figure not shown]
4. During the past seven days, how many hours did you actually work?

HOURS (*If "0", skip to question 6.*)

5. During the past seven days, how much did your health problems affect your productivity while you were working?

*Think about days you were limited in the amount or kind of work you could do, days you accomplished less than you would like, or days you could not do your work as carefully as usual. If health problems affected your work only a little, choose a low number. Choose a high number if health problems affected your work a great deal.*

Consider only how much health problems affected productivity while you were working.

[figure not shown]

CIRCLE A NUMBER

6. During the past seven days, how much did your health problems affect your ability to do your regular daily activities, other than work at a job?

*By regular activities, we mean the usual activities you do, such as work around the house, shopping, childcare, exercising, studying, etc. Think about times you were limited in the amount or kind of activities you could do and times you accomplished less than you would like. If health problems affected your activities only a little, choose a low number. Choose a high number if health problems affected your activities a great deal.*

Consider only how much health problems affected your ability to do your regular daily activities, other than work at a job.

CIRCLE A NUMBER

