## 5 TRIAL DESIGN

### 5.1 Full-scale study design

The overall objective of the foot drop trial is to test the superiority of surgical release of the peroneal nerve at 10 +/- 4 weeks after symptom onset to maximal conservative treatment. The FOOTDROP trial is designed as a prospective, multicenter, randomized, parallel-design study. A double-blind design is not possible, given the fact that both the treating physician and the patient will always know the allocated treatment strategy. The clinical researcher (= outcome assessor) will be blinded for treatment.

Subjects will be randomized 1:1 to surgery or conservative treatment (simple randomization based solely on a single, constant 1:1 allocation ratio). If a patient, that signed the informed consent form (ICF), cannot be randomised because the foot drop has recovered, this will be documented in the eCRF. After randomization, the patients allocated to conservative treatment will enter a treatment period of approximately 9 months (individualised physiotherapy program). Patients allocated to the surgical arm will undergo surgery as soon as feasible after randomization (maximum within 1 week, preferably within 2 days). For all participating patients that signed the informed consent at the screening visit, an operation day will be scheduled, maximum one week after the randomization visit (due to practical scheduling reasons). At the moment of scheduling, the patient will be unaware of this date to prevent bias (and orientation of the mindset of patients toward surgery). If a patient is allocated to the conservative arm of the trial, the scheduled operation date will be cancelled, without knowledge of the patient. To facilitate signing of the informed consent form at the screening visit, patients will be informed prior to the consultation about the study (by telephone, through the patient brochure).

Patients in the surgical arm of the trial, are allowed to follow physiotherapy after surgery. The frequency and intensity are to be determined by the treating physician. All participants are allowed to use an ankle-foot orthosis. The use of electrostimulation is not advised, although not forbidden.

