#### **8.7.15 Work Productivity and Activity Impairment Questionnaire: General Health (WPAI:GH)**

Health economic aspects of foot drop will be evaluated through the Work Productivity and Activity Impairment Questionnaire (WPAI). The WPAI is widely used and validated in multiple languages. The WPAI allows for assessment of employment and professional productivity among other features. Participants will fill in the WPAI at baseline, 6 weeks and 6 months. WPAI will be available online. If the patient receives allowances, the amount will be noted for economic analysis. This is not considered standard of care. The English version of the WPAI is included in Appendix 7.

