#### **8.7.16 Return to work at six weeks after randomization**

Health economic aspects will also be evaluated through the assessment of return to work. We expect subgroups of patients with foot drop to be unable to work. Once the foot drop has improved (or fully recovered), we expect patients to be able to return to work and to not experience any more related problems (after their initial recovery). In this trial population foot drop does in general not represent a chronic condition with periods of relapse. Either the foot drop recovers enough to be able to work again, or the foot drop does not sufficiently recover to resume previous professional activities.

Taking this into account, return to work seems to represent a very important measure. Patients will be asked about return to work at the study visit six weeks after randomization. To avoid recall bias, patients will be asked in advance to record the date of return to work. During baseline assessments, subjects will be questioned if they are incapacitated to work due to the foot drop and the last working day will be recorded in the eCRF.

We anticipate the biggest difference in return to work between the two groups at six weeks after randomization. We expect patients to recover faster after neurolysis. Therefore, we expect that a significant majority in the surgically treated group will be able to return to work six weeks after randomization (equals five to six weeks after surgery), whereas recovery could be slower in the conservative group. Recovery from surgery itself is generally fast, thus we do not expect that surgical recovery has a big impact on return to work but of course this issue will also be tackled in the trial.

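### The WPAI's seven-day recall misses the operation and at least the first three weeks after it, and the return-to-work items fill that gap only in part

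*Protocol*

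**What the plan says.** The WPAI form in Protocol Appendix 7 has a seven-day recall that leaves out the day of completion. Its absence item reads "During the past seven days, how many hours did you miss from work because of your health problems", followed by the instruction "Do not include time you missed to participate in this study". Section 8.7.15 sets the schedule: "Participants will fill in the WPAI at baseline, 6 weeks and 6 months". The procedures table (8.8) and section 11.5 agree with this. The 10-day post-operative contact collects the EQ-5D-5L but not the WPAI.

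Under section 5.1, surgery follows randomisation "maximum within 1 week, preferably within 2 days". Section 8.7.16 accordingly places the 6-week visit "six weeks after randomization (equals five to six weeks after surgery".

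The WPAI is not the only work measure. Sections 8.6 and 8.7.16 record employment at baseline and, for patients unable to work, the last day worked. Section 8.7.16 adds: "To avoid recall bias, patients will be asked in advance to record the date of return to work". That date is collected at 6 weeks. On the effect of surgical recovery on return to work, the same section expects little but says "of course this issue will also be tackled in the trial".

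Section 4.2 makes cost-effectiveness a secondary objective. Section 11.5 names a healthcare-payer base case and a societal perspective, and lists time lost from paid and unpaid work among the indirect costs. The economic analysis itself is left to a separate plan (11.4.6, 11.5).

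**The concern.** The operation is an event with its own short-term work cost (hospital attendance, wound healing, sick leave), and up to 9 months it occurs in one arm only. A questionnaire that samples single weeks can describe a slowly changing state. It cannot describe a short spell that falls wholly between two sampled weeks. If leave taken for surgery is in no recall window and is not fully recorded elsewhere, the societal analysis works with incomplete absenteeism in the weeks where the arms differ by design.

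The analysis plan can decide how to value lost time, but it cannot recover absence that was never recorded. The data collection is fixed in this protocol, which is why the point belongs here.

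**Working it through.** **Inputs.** Randomisation and baseline WPAI = day 0 (8.6, 8.8). Surgery on day s, with s = 0, 2 or 7 (5.1). The 6-week visit on day v: v = 42 nominally, v = 49 at the end of the +1 week window in 8.8, and v = 35 if that window were meant as ±1 week. Recall = 7 days, not counting the visit day (Appendix 7).

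**The protocol's own figure.** v − s = 42 − 7 = 35 days to 42 − 0 = 42 days, or five to six weeks after surgery. This agrees with 8.7.16.

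**Recall windows.** A WPAI on day v covers days v − 7 to v − 1.
- Baseline: days −7 to −1, before any operation.
- 6 weeks: days 35 to 41 (v = 42), 42 to 48 (v = 49) or 28 to 34 (v = 35).
- 6 months: about days 175 to 181.

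**Days from surgery outside any window** = (v − 7) − s:

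| Visit day v | s = 0 | s = 2 | s = 7 |
|---|---|---|---|
| 42 | 35 | 33 | 28 |
| 49 | 42 | 40 | 35 |
| 35 | 28 | 26 | 21 |

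Under every reading, at least the first three weeks from surgery, and up to six, are unobserved by the WPAI. The two post-baseline windows together cover 14 of about 182 days to 6 months (14/182 = 7.7%) and 14 of about 274 days to 9 months (14/274 = 5.1%).

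**What the other work items add in weeks 0 to 6:**

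| Patient | Start of absence | End of absence | Result |
|---|---|---|---|
| Off work at baseline, back by week 6 | Last working day | Return date | Complete spell in whole days, including post-operative time |
| Off work at baseline, not back by week 6 | Last working day | None recorded | Absence up to the visit can be inferred; its end is undated |
| Working at baseline, stops for the operation | Not expressly collected | Return date, if given | Start must be inferred from the surgery date |
| Working at baseline, conservative arm, stops later | Not expressly collected | Return date, if given | No surgery date to anchor the start |
| Part-time return, lost hours, unpaid work | – | – | Not measured in either arm |

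The rows for patients working at baseline should not be empty: 8.7.16 expects only subgroups to be unable to work.

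**The case against.** **There are other work measures.** This stands in part. A reader might infer from the WPAI calendar that surgery's productivity cost is simply not counted. The document does not support that: for a patient off work at baseline who is back by week 6, the two dates capture the post-operative absence in whole days. Section 8.7.15 also notes the amount of any allowances, though an amount is not a count of days or hours.

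**The remaining gap can be bridged.** The return-to-work question is not restricted to patients off work at baseline, and the surgery date is at most seven days from randomisation, so operative leave could be approximated when a return date is given. That is fair for whole days in the surgical arm. It does not give hours or part-time return, and the conservative arm has no equivalent anchor.

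**The direction of bias is unknown.** This stands in full. A reader might infer that the comparison is tilted in favour of surgery, because operative leave is one-sided. But the same weeks also hide absence due to foot drop in both arms, and 8.7.16 expects recovery could be slower under conservative care. Missing those weeks may conceal a cost of surgery, an early benefit of it, or both.

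**The promise about surgical recovery concerns return to work, not the WPAI.** Correct; the sentence in 8.7.16 does not contradict the WPAI schedule. It does state an aim that the listed items meet only for some patients.

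**The matter is peripheral.** The economic analysis has its own plan and a payer base case. That limits the consequence but does not remove the point, since section 11.5 is where the data for the societal analysis are fixed.

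**Conclusion.** The concern holds in a limited form. No WPAI window covers the operation or the first 21 to 42 days from it (28 to 35 with a visit on day 42). This rests only on the recall period, the visit schedule and the timing of surgery. The last-working-day and return-to-work items close the gap with a complete spell only for patients already off work at baseline who return by week 6. For patients still working at randomisation the start of absence is not expressly collected, and partial absence in weeks 0 to 5 is unmeasured in both arms.

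The number of working days missed cannot be derived from the document. One could assume 50–70% of 91 surgical patients employed, 40–60% of those still working, and 5–15 days of leave, giving 91 × 0.5 × 0.4 × 5 = 91 to 91 × 0.7 × 0.6 × 15 = 573 days. None of these inputs has an anchor in the protocol, the range is sixfold, and nothing is netted off for the conservative arm or for leave that the recorded dates would reveal. It should not be read as an estimate of bias.

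The consequence is confined to absenteeism in the societal-perspective analysis. The payer base case and the primary endpoint are unaffected.

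**What to change.** At 6 weeks, ask every patient employed at baseline, in both arms, for (a) the first day off work since randomisation, if any, and (b) the total working days or hours missed since randomisation for health reasons. Word it without reference to an operation, so that it reads the same in both arms. Add it to sections 8.7.16 and 8.8, and have the economic analysis plan use it, rather than the seven-day WPAI value, for absenteeism in weeks 0 to 6.

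Collect it in the online survey beside the return-to-work date. Online collection alone does not protect blinding: under 8.7 the blinded researchers may complete questionnaires that patients skip, and 8.8 assigns both work items to the blinded researcher or the patient. A first day off work close to randomisation could reveal the arm, so unblinded staff should complete this item when the survey is skipped.

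The cost is one extra item at an existing time point, with a six-week recall that is eased by the date patients are already asked to note. No visit or treatment changes.
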